11.1 Definitions and Standards

Adverse Event (AE):

Any untoward medical occurrence in a Participant involved in a clinical study administered a Study Product whether or not related to this product.

An AE can therefore be any unfavorable and unintended sign (including an abnormal laboratory finding for example), subjective and objective symptom, or disease temporally associated with the use of a product, accidents, whether or not considered related to the product or study-related procedure and reported by the Participant or observed by the PI/Sub-Investigator.

Serious Adverse Event (SAE):

Any AE that at any dose fulfils at least one of the following criteria:

1. Is fatal (results in death)
(note: death is an outcome, not an event)
2. is life-threatening
(note: the term “life-threatening” refers to an event in which the Participant was at risk of death at the time of the event; it does not refer to an event which could hypothetically have caused death had it been more severe)
3. requires inpatient hospitalization or prolongation of existing hospitalization
(note: “inpatient hospitalization” refers to an unplanned, overnight hospitalization)
4. results in persistent or significant disability/incapacity
(note: the term means substantial disruption of one’s ability to conduct normal life function)
5. is a congenital anomaly/birth defect
(note: congenital anomaly/birth defect in offspring of Participant taking the product regardless of time to diagnosis)
6. is medically significant
(note: Medical and scientific judgement should be exercised in deciding whether expedited reporting is appropriate in other situations, such as important medical events that may not be immediately life-threatening or result in death or hospitalization but may jeopardize the Participant or may require intervention to prevent one of the other outcomes listed in the definitions above)

Suspected Unexpected Serious Adverse Reaction (SUSAR)

A suspected Unexpected Serious Adverse Reaction is any adverse reaction for which the nature or severity is non consistent with the applicable product information.

11.2 Adverse event assessment

Expectedness:

An unexpected AE is an event of which the nature or severity is not consistent with the Participant’s medical history, concomitant medications, or the applicable product information.

For purposes of this study, bloating and mild diarrhea may be expected according to previous reports. All other AEs reported will be unexpected.

11.2.1 Causality Assessment

The causality assessment of an AE to the investigational and/or study procedure(s) product will be rated as follows:

Unrelated: The event is clearly related to other factors such as the Participant's clinical state, therapeutic interventions, or a concomitant medication administered to the Participant and does not follow a known response pattern to the Study Product.

Unlikely: The event follows a reasonable temporal sequence from the time of Study Product administration, although there is another plausible explanation for the occurrence of the event.

Possible: The event follows a reasonable temporal sequence from the time of Study Product administration and/or follows a known response pattern to the study treatment but could have been produced by other factors such as the Participant's clinical state, therapeutic interventions, or concomitant medications administered to the Participant.

Probable: The event follows a reasonable temporal sequence from the time of Study Product administration and follows a known response pattern to the Study Product, where the event is more likely explained by the product than any other cause.

Definite: The event follows a reasonable temporal sequence from the time of Study Product administration and follows a known response pattern to the Study Product and cannot be reasonably explained by other factors such as the Participants clinical state, therapeutic interventions administered to the Participant and either occurs immediately following Study Product, or improves on stopping the Study Product, or reappears on repeat exposure, or there is a positive reaction at the application site.

11.2.2 Severity/Intensity

The severity of AEs must be recorded, including the start and stop dates for each change in severity. An event that worsens / increases in severity should be captured as a new event. After initiation of IP consumption, worsening of events that started prior to initiating intake of IP must be recorded as new AEs (for example, if a patient experiences mild intermittent dyspepsia prior to dosing of IP, but the dyspepsia becomes severe and more frequent after first dose of IP has been administered, a new AE of severe dyspepsia [with the appropriate date of onset] is recorded in the eCRF).

The severity/intensity of AEs where applicable will be graded on a five-point-scale in accordance with the Common Terminology Criteria for Adverse Events:

Grade 1:	Mild AE - Discomfort noted, but no disruption to normal daily activities
Grade 2:	Moderate AE - Discomfort sufficient to reduce or affect normal daily activities
Grade 3:	Severe AE - Inability to work or perform normal daily activities
Grade 4:	Life threatening or disabling AE
Grade 5:	Death related to AE

11.2.3 Outcome of event

The outcome of AEs must be followed up and recorded during the course of the study in the eCRF.

Outcomes are as follows:

- Recovered
- Recovered with sequelae
- Ongoing
- Fatal
- Unknown/Lost to follow-up

11.2.4 Clinical laboratory and other safety evaluations

A change in the value of a clinical laboratory, vital sign, or other study assessment can represent an AE if the change is a clinically significant worsening from baseline. This includes abnormal assessments where there is a shift of a parameter from a normal value to an abnormal value, or a significant worsening of an already abnormal value. Clinical significance is defined as an abnormal study assessment that leads to a diagnosis (in which case the diagnosis is recorded rather than the abnormal assessment) or results in Participant intervention such as further monitoring (excluding confirmatory repeat testing) or medical treatment. If, at the end of the treatment phase, there are abnormal clinical laboratory, vital sign values or other study assessments which were not present pre-treatment, the value observed closest to the start of study treatment should be used as baseline. The PI or Sub-Investigator should decide, based on the above criteria and the clinical condition of a Participant, whether a worsening of an abnormal study assessment is clinically significant and therefore represents an AE.

11.3 Pregnancy

All pregnancies are to be reported from the time of enrolment to the end of follow-up in the Participants eCRF and reported using a Pregnancy Report Form. Any report of pregnancy for any study Participant must be reported to the Sponsor. Pregnancy itself is not an AE, however it should be reported for tracking purposes.

Pregnant Participants must be withdrawn from using the Study Product, and in consultation with the Sponsor and/or PI/Sub-Investigator may be withdrawn from the study or asked to remain and continue safety monitoring for the remainder of the study. Every effort should be made to gather information regarding the pregnancy outcome.

The Participant will be asked to notify the PI/Sub-Investigator of the outcome of the pregnancy (i.e., birth, loss, or termination). To help ensure this, the PI/Sub-Investigator will follow-up with the Participant until the end of pregnancy or last study Visit whichever occurs first, with the Participant's consent. This request and the Participant's response will be documented in the Participant's source document. Pregnancy outcome will be determined as live birth, still birth or pregnancy termination.

If the pregnancy is due to a Participant's failure to comply with the contraceptive requirements of the protocol, this should also be documented as a protocol deviation.

Pregnancy complications such as spontaneous abortion/miscarriage or congenital abnormality are considered SAEs and must be reported as such. Note: an elective abortion is not considered an SAE. In addition to the above, if the PI/Sub-Investigator determines that the pregnancy meets SAE criteria, it must be reported as an SAE. The test date of the first positive urine human chorionic gonadotropin test or ultrasound result will determine the pregnancy onset date.

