The eCRFs for any Participant leaving the study should be completed at the time of the final Visit or shortly thereafter. Any ongoing AEs at the final Visit will be characterized as 'Ongoing at End of Study' and there will be no further follow up.

11 Safety and Tolerability

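### Section 11.3 ends the only specified investigator follow-up of a pregnancy at the last study visit, before any live birth, still birth or anomaly seen at birth

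*Protocol*

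**What the plan says.** Protocol section 11.3 sets three aims for a pregnancy reported during the study.

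- On effort: "Every effort should be made to gather information regarding the pregnancy outcome".
- On the categories: "Pregnancy outcome will be determined as live birth, still birth or pregnancy termination".
- On safety reporting: "Pregnancy complications such as spontaneous abortion/miscarriage or congenital abnormality are considered SAEs and must be reported as such". Section 11.1 lists a birth defect among the SAE criteria and notes that this covers a "congenital anomaly/birth defect in offspring of Participant taking the product regardless of time to diagnosis".

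The means are narrower. The participant is asked to tell the investigator the outcome, and "This request and the Participant's response will be documented in the Participant's source document". To support that request, and with the participant's consent, "the PI/Sub-Investigator will follow-up with the Participant until the end of pregnancy or last study Visit whichever occurs first". A pregnant participant stops the product and "may be withdrawn from the study or asked to remain and continue safety monitoring for the remainder of the study".

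Section 10.1.2 adds: "The eCRFs for any Participant leaving the study should be completed at the time of the final Visit or shortly thereafter". It also says that adverse events still ongoing at the final visit are not followed further. The schedule in section 6 (Table 2) puts Visit 3 at Day 56 with a window of 3 further days, and shows no contact after it.

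**The concern.** The follow-up is there to make sure the outcome is learned, but its stopping rule ends it before two of the three listed outcomes can occur. An eight-week intervention is much shorter than a pregnancy, and women already pregnant are kept out by section 4.4 and the urine tests at Visits 1 and 2. Unless the pregnancy ends early, the last visit is always the earlier of the two stops. It makes no difference whether the woman is withdrawn or asked to stay, since staying lasts only to the end of the study.

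What is at stake is safety capture. For a live birth, a still birth or an anomaly seen at birth, the outcome record and any SAE report would depend on the participant volunteering the information months later, with no specified prompt from the site. The protocol treats an anomaly as an SAE whenever it is diagnosed, but ends the one specified contact likely to reveal it.

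**Working it through.** **The plan's own figures.** Section 3.2 gives up to 7 days of screening, 14 of run-in and 56 of intervention: 7 + 14 + 56 = 77 days, or 11 weeks. This matches its stated total. The latest Visit 3 in Table 2 is Day 56 + 3 = Day 59.

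**Assumptions, not in the documents.**

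- The last menstrual period falls 14 days before conception, and term is 280 days from it.
- A urine test misses at most the first 14 days after conception, so a conception before Day -14 is found by Visit 2 (Day 0) and excluded.
- A still birth is counted from 20 to 28 weeks (140 to 196 days).

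**Formulas.** Gestation at the last visit = 14 + (59 − conception day). Shortfall to term = 280 − gestation.

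| Conception | Gestation at Day 59 | Days short of term |
|---|---|---|
| Day -14 | 14 + 73 = 87 d (12.4 wk) | 280 − 87 = 193 |
| Day 1 (first dose) | 14 + 58 = 72 d (10.3 wk) | 280 − 72 = 208 |
| Day 45 (14 days before the visit) | 14 + 14 = 28 d (4.0 wk) | 280 − 28 = 252 |
| Day 59 (day of the visit) | 14 + 0 = 14 d (2.0 wk) | 280 − 14 = 266 |

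In the most advanced case the still-birth threshold lies 140 − 87 = 53 to 196 − 87 = 109 days after the stop. A first positive test at Visit 3 leaves 0 days of follow-up.

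**Sensitivity.**

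- Visit 3 on Day 56: 14 + 14 + 56 = 84 days, and 280 − 84 = 196 days short of term.
- Conception on the earliest Visit 1 day (Day -21), missed at Visit 2: 14 + 80 = 94 days (13.4 weeks), 186 days short.
- Conception two weeks before that (Day -35), missed at both early tests: 14 + 94 = 108 days (15.4 weeks), 172 days short.
- Visit 3 delayed by the whole 14-day spare supply (sections 5.3 and 5.5.1) to Day 70, conception on Day -14: 14 + 84 = 98 days (14.0 weeks), 182 days short.

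None of these reaches 20 weeks. Early withdrawal only brings the stop forward.

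**Other provisions that might fill the gap.** Section 11.2.3 follows adverse event outcomes during the study. Section 11.5 ties adverse event collection to scheduled visits and telephone calls. Neither specifies a contact after Visit 3, and Table 2 lists none.

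**The case against.** The strongest reply is that section 11.3 does not contradict itself. Only the active contact has an end date. The effort sentence and the participant's notification have none, and because the notification expressly covers birth, it is meant to reach past the study. On this reading the section 11.1 note defines what counts as an SAE and sets no surveillance period. Once an event is known, section 11.5 has the CRO report it to the sponsor within 24 hours of becoming aware, and separate Pregnancy Report and SAE forms exist whatever happens to the eCRF. Stopping at the last visit also matches the general adverse event policy in section 10.1.2. It may be proportionate for a product described as long used in foods and supplements, in a trial that requires contraception. The consent pages, the Pregnancy Report Form and the Safety Monitoring Plan are not shown and may cover later contact.

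Much of this stands. Recording a late outcome is not forbidden, the duty to report a known SAE does not lapse, and a miscarriage or termination before the last visit can be captured. The exact day counts rest on outside assumptions.

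It does not remove the point. Every surviving provision works only once someone at the site learns the outcome, and no contact is specified after Visit 3 to learn it. The effort sentence has no method, schedule or end point, while the specific stopping rule has one and points the other way. Documents not shown could add contact, but they would not correct the protocol sentence.

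**Conclusion.** The concern holds, as a minor one. For any continuing pregnancy that arises in the study, the specified investigator follow-up stops at the last visit. At that point gestation is at most 12.4 weeks under the main assumptions, and about 15 weeks in the most extreme case tried. Term is 193 to 266 days away under the main assumptions. The day counts depend on the assumed dating, test sensitivity and still-birth threshold. The conclusion that live birth, still birth and anomalies seen at birth fall after the stop does not change in any variation tried.

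Few or no participants should be affected, with 80 randomized and contraception required. The primary endpoint, its analysis and the sample size are not touched.

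**What to change.** In section 11.3, delete the last-visit alternative from the follow-up sentence, so that the investigator follows the participant to the end of pregnancy, with her consent, even when that is after the last study visit. A short clarifying sentence could add that an outcome learned after the last visit still goes on the Pregnancy Report Form, and on the SAE Form if it meets SAE criteria. This second part largely restates existing duties; the deletion is the change that matters.

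The cost is a small amendment with IRB/IEC approval (section 12.5), possibly consent wording for post-study contact, and one or a few remote contacts for each affected participant. Visits, efficacy data and sample size stay as they are.

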11.4 Safety Management

11.4.1 Procedures

All Adverse Events (AEs) occurring during clinical studies are recorded in the electronic Case Report Form (eCRF).

Serious adverse events (SAEs) are reported and processed according to the applicable laws and regulatory requirements governing the conduct of clinical studies. SAEs must be recorded on the SAE Form.

11.5 Responsibilities

PI or Sub-Investigator will ensure that SAE reporting procedures outlined in the study protocol are adhered to and that all required documentation is up-to-date, and that regulatory and IRB/IEC SAE reporting procedures are followed.

All clinical research personnel at the study site (PI, Sub-Investigator, Project Manager, Clinical Research Coordinator, Clinical Trial Assistant, Research Nurse, Phlebotomist) who are in contact with Participants are responsible for collecting AE information from the Participant at each scheduled site visit or during telephone calls with the Participant. Therefore, Sponsor clinical research personnel or a delegate (e.g. CRO) who initiate and monitor the study are responsible for explaining the procedures for reporting and evaluating AEs to the PI or Sub-Investigator and all study personnel who come in contact with the Participants

During the course of the study, complete reports of all AEs will be entered in the Participants site source documents, and if applicable, on the appropriate study case report forms (CRFs).

A licensed clinician will be responsible for:

- identifying and evaluating the severity (mild, moderate, or severe) and clinical importance of the AE,
- taking appropriate medical action(s), and for
- notifying the Sponsor immediately of an SAE as specified in the protocol and for notifying the Science Department for reporting to the IRB/IEC.

Likewise, a licensed clinician will indicate the causality (relationship) of the AE to the Study Product and modify IP consumption in the event of a safety concern.

For any laboratory abnormality, the PI or Sub-Investigator will make a judgement as to its clinical significance. If the laboratory value is thought to be clinically significant, the Sponsor may be consulted, and an assessment will be made by the PI or Sub-Investigator as to its relationship to Study Product administration and it will be documented on the AE page of the CRF.

The PI or Sub-Investigator will comply with applicable regulatory requirement(s) related to the reporting of SAEs to the IRB/IEC.

The Monitor(s) will review completed CRF data and will compare CRF entries with information recorded in the source documents. Any discrepancies or omissions in either data source will be discussed with the site personnel who should make the appropriate corrections to the documents.

The CRO will report all SAEs to the Sponsor within 24 hours of becoming aware of the event, whether or not the SAE is considered to be related to the Study Product. All clinically relevant SAEs will be reported to the Clinical Research Ethics Committee of the Cork Teaching Hospitals.

12 Ethical Considerations

12.1 Local Regulations and Declaration of Helsinki

The PI/Sub-Investigator will ensure that this clinical study is conducted in line with the principles of the “Declaration of Helsinki” and/or with the laws and regulations of the country in which the research is conducted, whichever affords the greater protection to the individual.

The site, investigator, protocol, informed consent form and any other pertinent documents for this study will be approved by the IRB.

The study will not begin until the IRB has approved of the protocol and the Participant consent form along with any advertisements, diaries, and instructions to the Participants, if applicable. The IRB approval will be documented in writing to the PI/Sub-Investigator.

12.2 GCP Management Directive

The PI/Sub-Investigator will ensure that this clinical study is conducted in line with the principles of GCP, as outlined below:

- Clinical studies should be conducted in accordance with the ethical principles that have their origin in the Declaration of Helsinki, and that are consistent with the principles of GCP (where applicable) and the applicable laws and regulatory requirements governing the conduct of human studies.
- Foreseeable risks and inconveniences should be weighed against the anticipated benefit for the individual trial Participant and the society.
- The rights, safety, and well-being of the Participants involved in clinical studies are the most important considerations and should prevail over interests of science and society.
- The available nonclinical and clinical information on any Study Product should be adequate to support the proposed clinical trial.
- Clinical studies should be scientifically sound, and described in a clear, detailed protocol.
- Clinical studies should be conducted in compliance with the protocol that has received prior institutional review board (IRB)/independent ethics committee (IEC) approval/favorable opinion.

- The medical care given to, and medical decisions made on behalf of, Participants involved in clinical studies should always be the responsibility of a qualified licensed clinician.
- Each individual involved in conducting clinical studies should be qualified by education, training, and experience to perform his or her respective task(s).
- Freely given written informed consent should be obtained from every Participant prior to participation in a clinical trial.
- All information from clinical studies should be recorded, handled, and stored in a way that allows its accurate reporting, interpretation, and verification.
- The confidentiality of records that could identify Participants should be protected, respecting the privacy and confidentiality rules in accordance with the applicable laws and regulatory requirements.
- Study Product should be manufactured, handled, and stored in accordance with Morinaga Milk Industry quality standards, or if applicable, good manufacturing practice (GMP); IP(s) should be used in accordance with the approved protocol.
- Systems with processes and procedures (such as SOPs) that assure the quality of every aspect of clinical studies should be implemented.

12.3 Informed Consent

It is the responsibility of the PI, or a person designated by the PI (if acceptable by local regulations), to obtain written informed consent from each Participant involved in this clinical study, or from the Participant's legally acceptable representative, after adequate explanation of the aims, methods, anticipated benefits, and potential hazards of the study. No study procedures may be performed prior to obtaining the informed consent. The PI or Designee must also explain that the Participants are completely free to refuse to enter the study or to withdraw from it at any time, for any reason.

12.4 IRB/IEC approval

This protocol and any accompanying material provided to the Participant (such as Participant information leaflets or descriptions of the study used to obtain informed consent) as well as any advertising or compensation given to the Participants, will be submitted by the PI/Sub-Investigator to an IRB/IEC. Approval from the IRB/IEC will be obtained before starting the study and should be documented in a letter to the PI/Sub-Investigator specifying the date on which the IRB/IEC met and granted the approval.

Any modifications (amendments) made to the protocol after receipt of the IRB/IEC approval must also be submitted by the PI/Sub-Investigator to the IRB/IEC in accordance with local procedures and regulatory requirements.

